#### **2.5.4.2.2. Sensitivity Analysis**

Analyses of the primary endpoints will be performed based on the FAS, using the same method and same definition as described in [Section 2.5.4.2.1](#).

This sensitivity analysis corresponds to the Supportive Immune Estimands 1b-3b as described in [Appendix I](#), Table 9.

#### 2.5.4.2.3. Supportive Analysis

A supportive analysis will be conducted to mitigate the potential power reduction due to the IRT error described in [Section 2.3.4](#). The primary immunogenicity endpoints of GMT and SRR, based on serum RSV-A nAbs at Day 29, will be analyzed on the Supportive PP Set.

The definition of Supportive PP Set can be found in [Section 2.4.3](#). It is estimated that approximately 180 participants in the Per-protocol Immunogenicity Set from mRNA-1345-P301 will be included, along with Group 1 and Group 2 participants in Per-protocol Set from mRNA-1345-P302 to form the Supportive PP Set. The participants from mRNA-1345-P301 and the Group 1 participants from mRNA-1345-P302 will be pooled together and compared with the Group 2 participants from mRNA-1345-P302.

This supportive analysis will be conducted when Part A database is locked and the immunogenicity data for participants in the Supportive PP Set is available. The corresponding Estimand is 1c as described in [Appendix I, Table 9](#). The same definition for the endpoints and the same statistical methods as described in [Section 2.5.4.2.1](#) will be applied in this supportive analysis.

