### **Supportive PP Set**

The Supportive PP Set consists of all Group 1 and Group 2 participants in the PP Set from mRNA-1345-P302 and participants from mRNA-1345-P301 who are in the Per-protocol Immunogenicity Set, received one injection of mRNA-1345 (█ CC1 µg) during April to June of 2022, and were in the Phase 3 segment from U.S sites. Please refer to Section 5.5 of mRNA-1345-P301 SAP for detailed definition of the Per-protocol Immunogenicity Set. The Supportive PP Set will be the analysis set for a supportive analysis of the primary immunogenicity endpoints of RSV-A nAbs and the key secondary immunogenicity endpoints of RSV-B nAbs to mitigate the IRT error as indicated in [Section 2.3.4](#). The participants from mRNA-1345-P301 and the Group 1 participants from mRNA-1345-P302 will be pooled together and compared with the Group 2 participants from mRNA-1345-P302.

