#### 2.5.4.2.1. Primary Analysis Approach

The co-primary endpoints include the following:

- GMT of serum RSV-A nAbs at Day 29
- SRR of serum RSV-A nAbs at Day 29
- GMT of serum influenza anti-HA Abs for each influenza strain (A/Victoria, A/Cambodia, B/Victoria, B/Phuket) at Day 29

The statistical analyses are:

- For the co-primary endpoints 1) and 3), the GMT ratio (GMR) between coadministered group and mRNA-1345 plus placebo group or between coadministered group and Afluria Quadrivalent plus placebo group will be estimated using an ANCOVA model on the log-transformed tiers at Day 29, with the vaccination group as the fixed variable, log-transformed baseline titers as a fixed covariate, adjusted for randomized age group. The GLSM for each vaccination group and its corresponding 95% CI in a log-transformed scale will be estimated from the model and back-transformed to obtain the estimates in the original scale as an estimate of the GMT and its 95%CI. The GMR will be estimated by the ratio of the GLSMs and the corresponding 2-sided 95% CI to assess the treatment difference. The noninferiority of the GMT will be demonstrated if the LB of the 95% CI of the GMR is  $> 0.667$  based on the noninferiority margin of 1.5.
- For the primary endpoint 2), SRR for RSV-A nAbs at Day 29 will be provided with 2-sided 95% CIs using the Clopper-Pearson method. The SRR difference between coadministered group and mRNA-1345 plus placebo group at Day 29 will be provided with 2-sided 95% CIs using the Miettinen-Nurminen's method. The noninferiority of the SRR will be demonstrated if the LB of the 95% CI of the SRR difference is  $> -10\%$  based on the noninferiority margin of 10%.

The study is considered to meet the primary immunogenicity objective if the noninferiority of the immune response to mRNA-1345 coadministered with Afluria Quadrivalent based all the co-primary endpoints.

The above analysis corresponds to the Primary Immune Estimands 1a-3a as described in [Appendix I](#), Table 9.

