#### 2.5.4.3. Analysis of the Key Secondary Immunogenicity Endpoints

The key secondary endpoints include the following:

- 1) GMT of serum RSV-B nAbs at Day 29
- 2) SRR in serum RSV-B nAbs at Day 29
- 3) SCR in serum influenza anti-HA Abs for each influenza strain (A/Victoria, A/Cambodia, B/Victoria, B/Phuket) at Day 29

The statistical analyses are:

- GMT of RSV-B nAbs at Day 29 will be analyzed using the same ANCOVA model as for RSV-A nAbs at Day 29. The GLSM for each vaccination group and GMR between coadministered group and mRNA-1345 plus placebo group and associated 95% CIs will be estimated from the ANCOVA model.
- SRR in RSV-B nAbs at Day 29 will be provided with 2-sided 95% CIs using the Clopper-Pearson method. The SRR difference between coadministered group and mRNA-1345 plus placebo group at Day 29 will be provided with 2-sided 95% CIs using the Miettinen-Nurminen's method.
- SCR in anti-HA Abs for each influenza strain at Days 29 will be provided with 2-sided 95% CIs using the Clopper-Pearson method. The SCR difference between coadministered

group and Afluria Quadrivalent plus placebo group at Day 29 will be provided with 2-sided 95% CIs using the Miettinen-Nurminen's method.

The key secondary endpoints of GMT and SRR, based on serum RSV-B nAbs at Day 29, will also be analyzed on the Supportive PP Set.

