**Table 9: Summary of Primary Immune Estimands with Rationale for Strategies to Address Intercurrent Events (Part A)**

Objective: To evaluate the impact of coadministered influenza vaccine on the immune response to RSV		
Estimand Label	Primary Immune Estimand 1a (on the PP Set)	Supportive Immune Estimand 1b (on the FAS Set)
Estimand Description	Immune response to RSV measured as GMR of RSV-A neutralizing Ab at Day 29 in adults $\geq$ 50 years old who receive IP administration and complied with immunogenicity blood sampling to have a baseline and at least 1 Day 29 assessment without major protocol deviations impacting immune response.	Immune response to RSV measured as GMR of RSV-A neutralizing Ab at Day 29 in adults $\geq$ 50 years old who receive IP administration irrespective of any major protocol deviations impacting immune response and complied with immunogenicity blood sampling to have a baseline and at least 1 Day 29 RSV-A neutralizing Ab assessment.
Target Population	Adults aged 50 years or older who receive the assigned IP administration, complied with immunogenicity blood sampling to have a baseline and at least 1 Day 29 RSV-A neutralizing Ab assessment after the IP administration, and have no major protocol deviations impacting the immune response.	Adults aged 50 years or older who receive any IP administration and complied with immunogenicity blood sampling to have a baseline and at least 1 Day 29 RSV-A neutralizing Ab assessment.
Endpoint	GMT of RSV-A neutralizing Ab at Day 29 (see Section 2.5.4.2.1).	As per Estimand 1a.
Treatment Conditions	mRNA-1345 + Afluria Quadrivalent (Test) vs. mRNA-1345 plus placebo (Reference)	As per Estimand 1a.

Population-Level Summary	Immune response to RSV defined as GMR of RSV-A neutralizing Ab using an ANCOVA model on the log-transformed tiers at Day 29, with the vaccination group as the fixed variable, adjusted for stratified age group used for randomization and log-transformed baseline tiers.	As per Estimand 1a.
Intercurrent Event Strategy		
IcEv1 (early discontinuation or unrelated death)	Principal stratum	Principal stratum
IcEv2 (Alternative flu vaccine)	Principal stratum	Treatment policy
IcEv3 (Prohibited medications)	Principal stratum	Treatment policy

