Rationale for Strategies	This estimand seeks to understand immune response impact during the coadministered influenza vaccine in adults aged 50 or older who receive the IP administration and comply with key protocol criteria.  A principal stratum is used for early discontinuation, unrelated deaths and major deviations (such as use of alternative vaccines and prohibited medications) so that analysis is a sub-population composed of participants free from intercurrent events.	A treatment policy strategy is used for following up immune response including all participants vaccinated irrespective of whether they subsequently were found not to strictly meet the key protocol criteria (i.e., major protocol deviations affecting immune response, use of the alternative flu or RSV vaccine, or use of the prohibited medications). There is interest in understanding immune response in the light of poor compliance which may happen in clinical practice and may reflect reactions to the IP administration as well as poor compliance for unrelated reasons.  The principal stratum is employed for the other intercurrent events which match Estimand 1a.
Estimand Label	Supportive Immune Estimand 1c (on the Supportive PP Set)	

Estimand Description	Immune response to RSV measured as GMR of RSV-A nAbs at Day 29 in [1] adults $\geq$ 50 years old who from mRNA-1345-P302 and receive IP administration and complied with immunogenicity blood sampling to have a baseline and at least 1 Day 29 assessment without major protocol deviations impacting immune response, or [2] adults $\geq$ 60 years old who in Per-protocol Immunogenicity Set from mRNA-1345-P301, receive one injection of mRNA-1345 (redacted $\mu$ g) during April to June of 2022, and in the Phase 3 segment from U.S. sites.		
Target Population	Adults aged 50 years or older who receive the assigned IP administration, complied with immunogenicity blood sampling to have a baseline and at least 1 Day 29 RSV-A neutralizing Ab assessment after the IP administration, and have no major protocol deviations impacting the immune response.		
Endpoint	As per Estimand 1a.		
Treatment Conditions	Test group of mRNA-1345 + Afluria Quadrivalent in mRNA-1345-P302 vs. Reference group of mRNA-1345 plus placebo in mRNA-1345-P302 or mRNA-1345 without placebo in mRNA-1345-P301		
Population-Level Summary	As per Estimand 1a.		
Intercurrent Event Strategy			

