IcEv3 (Prohibited medications)	Principal stratum	Treatment policy

Rationale for Strategies	
This estimand seeks to understand immune response impact during the coadministered influenza vaccine in adults aged 50 or older who receive the IP administration and comply with key protocol criteria.
 
A principal stratum is used for early discontinuation, unrelated deaths and major deviations (such as use of alternative vaccines and prohibited medications) so that analysis is a sub-population composed of participants free from intercurrent events.
	
A treatment policy strategy is used for following up immune response including all participants vaccinated irrespective of whether they subsequently were found not to strictly meet the key protocol criteria (i.e., major protocol deviations affecting immune response, use of the alternative flu or RSV vaccine, or use of the prohibited medications). There is interest in understanding immune response in the light of poor compliance which may happen in clinical practice and may reflect reactions to the IP administration as well as poor compliance for unrelated reasons.
 
The principal stratum is employed for the other intercurrent events which match Estimand 2a.

Estimand Label	Primary Immune Estimand 2c (on the Supportive PP Set)	
Estimand Description	Immune response to RSV measured as SRR difference of RSV-A neutralizing Ab at Day 29 in [1] adults $\geq$ 50 years old who from mRNA-1345-P302 and receive IP administration and complied with immunogenicity blood sampling to have a baseline and at least 1 Day 29 assessment without major protocol deviations impacting immune response, or [2] adults $\geq$ 60 years old who in Per-protocol Immunogenicity Set from mRNA-1345-P301, receive one injection of mRNA-1345 (█ μg) during April to June of 2022, and in the Phase 3 segment from U.S. sites.	
Target Population	Adults aged 50 years or older who receive the assigned IP administration, complied with immunogenicity blood sampling to have a baseline and at least 1 Day 29 RSV-A neutralizing Ab assessment after the IP administration, and have no major protocol deviations impacting the immune response.	
Endpoint	As per Estimand 2a.	
Treatment Conditions	Test group of mRNA-1345 + Afluria Quadrivalent in mRNA-1345-P302 vs. Reference group of mRNA-1345 plus placebo in mRNA-1345-P302 or mRNA-1345 without placebo in mRNA-1345-P301	

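### Part A Supportive PP Set: the RSV seroresponse differences are not age-stratified although P301 participants, all 60 or older, join only the reference side, and the ANCOVA age term is not specified for them

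*SAP*

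**What the plan says.** **The set.** SAP 2.4.3 defines the Supportive PP Set as Groups 1 and 2 from the PP Set plus selected P301 recipients of mRNA-1345. The P301 participants and "the Group 1 participants from mRNA-1345-P302 will be pooled together and compared with the Group 2 participants". SAP 2.5.4.2.3 expects about 180 from P301. Estimands 1c and 2c (SAP Appendix I, Table 9) describe them as adults of at least "60 years old who in Per-protocol Immunogenicity Set from mRNA-1345-P301".

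**The methods.** SAP 2.5.4.2.3 states: "The same definition for the endpoints and the same statistical methods as described in" SAP 2.5.4.2.1. That section contains two:
- GMT: an ANCOVA with "log-transformed baseline titers as a fixed covariate, adjusted for randomized age group". Estimand 1c takes its summary from Estimand 1a, which is "adjusted for stratified age group used for randomization and log-transformed baseline tiers".
- SRR: the "SRR difference between coadministered group and mRNA-1345 plus placebo group at Day 29 will be provided with 2-sided 95% CIs" by the Miettinen-Nurminen method, with no stratification factor named. Estimand 2c is the matching estimand: "Immune response to RSV measured as SRR difference of RSV-A neutralizing Ab at Day 29 in [1] adults".

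SAP 2.5.4.3 extends this to RSV-B: the key secondary GMT and SRR endpoints, "based on serum RSV-B nAbs at Day 29, will also be analyzed on the Supportive PP Set".

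**Age elsewhere in the SAP.** Part A randomisation strata are 50-59, 60-74 and 75 or older, with about 20% targeted at 50-59 (SAP 2.3.1, 2.3.4). In SAP 2.5.2.2, a general paragraph lists randomised and actual age group in those bands and names the Supportive PP Set among the sets summarised. The next paragraph, specific to this set, uses 50-59, 60-69, 70-79 and 80 or older. SAP 2.5.4.6 allows, but does not require, subgroup analyses that include 60 or older.

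**The concern.** The primary Group 1 versus Group 2 comparison has age-stratified randomisation behind it. The supportive comparison does not: its reference side gains a block of people with nobody aged 50-59, and Group 2 gains nothing to match. If SRR differs by age, an unstratified difference mixes the effect of coadministration with a difference in age mix. The GMT analysis on the same set would adjust for age; the SRR analysis would not.

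The GMT analysis has a gap of its own. P301 participants have no P302 randomisation stratum, and neither document says which age group they take. SAP 2.5.1 does not impute missing values other than dates unless a rule is given. Read literally, an ordinary ANCOVA could drop the very participants who were added to restore power. The decade bands in SAP 2.5.2.2 do not settle it, because 70-79 straddles the 75-year cut.

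This set is the plan's stated mitigation of the IRT error, so its results will be read as backing for the RSV-A and RSV-B conclusions.

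**Working it through.** **Inputs from the documents.** Group 1 randomised: about 250 (SAP 2.3.4). Total: about 1620. PP exclusion: 10%. P301 add-on: about 180. Share aged 50-59: about 20% (a target). SRR 80% in both groups, 10-point margin, two-sided alpha 0.05, SD of log titre 1.5 (SAP 2.3.3).

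**The plan's own power.** The SAP gives none for the Supportive PP Set, so the check is on the planned 378 versus 540.
- SRR: SE = √(0.16/378 + 0.16/540) = 0.0268; Φ(0.10/0.0268 − 1.96) = 96.1%. Stated: 96%.
- GMT: SE = 1.5 × √(1/378 + 1/540) = 0.1006; Φ(ln 1.5/0.1006 − 1.96) = 98.1%. Stated: 98%.

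Both reproduce.

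**Sizes after the IRT error (assumed).** Group 1 PP = 250 × 0.9 = 225. Group 2 = (1620 − 250)/2 = 685, and 685 × 0.9 ≈ 616. Reference side = 225 + 180 = 405, of which 180/405 = 44% is from P301.

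| Comparison | SRR power (normal approx.) | GMT power |
|---|---|---|
| 225 vs 616 | 89.4% | 93.4% |
| 405 vs 616 | 97.4% | 98.8% |

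Pooling therefore does what it was meant to do for power.

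**Age mix.** Aged 50-59 on the reference side: 0.20 × 225 = 45, and 45/405 = 11.1%. In Group 2: 20%. Difference: 0.089.

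**Bias.** With the same true difference d in every age group, the crude difference has expectation d + 0.089 × g, where g = SRR(50-59) − SRR(60 or older). The documents do not give g. The table uses assumed values with overall SRR held at 80% at Group 2's age mix, and 200,000 simulated trials per row. Error is one-sided at a true difference of −10 points (nominal 2.5%). Power is at a true difference of 0. The stratified interval is Miettinen-Nurminen with Mantel-Haenszel weights over 50-59 and 60 or older.

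| g (points) | Bias (points) | Error, crude | Error, stratified | Power, crude | Power, stratified |
|---|---|---|---|---|---|
| −20 | −1.78 | 0.4% | 2.5% | 92.1% | 98.4% |
| −10 | −0.89 | 1.1% | 2.6% | 95.7% | 98.0% |
| −5 | −0.44 | 1.8% | 2.6% | 96.9% | 97.9% |
| 0 | 0 | 2.6% | 2.6% | 97.9% | 97.7% |
| +5 | +0.44 | 3.7% | 2.6% | 98.6% | 97.6% |
| +10 | +0.89 | 5.1% | 2.5% | 99.1% | 97.6% |
| +20 | +1.78 | 9.4% | 2.6% | 99.7% | 97.5% |

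Hand check at g = +10: SE at 70% versus 80% = √(0.21/616 + 0.16/405) = 0.0271; Φ(0.0089/0.0271 − 1.96) = 5.1%.

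**Sensitivity of the 0.089.** With 120 P301 participants: 0.20 − 45/345 = 0.070. With 240: 0.20 − 45/465 = 0.103. With a 15% share aged 50-59: 0.15 − 33.75/405 = 0.067.

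**The case against.** The case for leaving the plan alone has several parts.

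- **No decision rests on this set.** It lies outside the testing hierarchy in SAP 2.5.5. This stands, and it limits the stakes. Appendix I labels 2c a primary estimand, from which a reader might infer that it counts towards success. SAP 2.5.4.2 and 2.5.4.2.3 treat the analysis as support only, so that inference fails.
- **The bias depends on a gap nobody has stated.** This stands. A gap of 5 points moves the estimate by 0.4 points. The 9.4% error rate needs a 20-point gap, that is, 96% at 50-59 and 76% at 60 or older. It should not be quoted as the expected size.
- **The ANCOVA gap is only a clarification.** Largely right. A reader might infer that the model cannot be fitted. The documents do not support that: age is summarised for P301 participants, and the stratum is simply not specified here.
- **The optional 60-or-older subgroup already answers it.** In part. It removes the 50-59 imbalance, but it is a may, it drops 45 + 123 = 168 participants (power about 95%), and it leaves the planned SRR estimate uncorrected.
- **Reusing the primary method keeps results comparable, and P301 was restricted to US Phase 3 participants dosed April to June 2022.** Both are sensible. They argue for keeping the unstratified interval in view, not against adding a stratified one.

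A reader might also extend the concern to the primary comparison, since Group 1 closed at 959 randomised and about (1620 − 959)/2 = 330 of 685 Group 2 participants, 48%, came later. The documents show no age imbalance there.

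**Conclusion.** The concern holds for the Supportive PP Set. The plan builds in an age imbalance of about 11% versus 20% aged 50-59 and leaves the RSV-A and RSV-B SRR differences unadjusted for it, and it does not say which age group P301 participants take in the ANCOVA. The first result rests on approximate counts, the 10% exclusion assumption and the 20% target; the second needs no numerical assumption.

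The size is modest and its direction unknown: nil without an age effect, under 1 point of the 10-point margin for a gap of 10 points or less, and 1.8 points for a gap of 20. If younger adults respond better, the supportive result looks too reassuring; if worse, too pessimistic. This is a cheap improvement to a supportive analysis. It does not threaten the Part A conclusion, and it does not reach Part B or the Group 2 versus Group 3 seroconversion comparison.

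**What to change.** In SAP 2.5.4.2.3, 2.5.4.3 and Estimands 1c and 2c:

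1. Define age group for every Supportive PP Set participant, P301 included, from actual age in the P302 bands (50-59, 60-74, 75 or older). Add those bands to this set's display in SAP 2.5.2.2, and use the variable in the ANCOVA in place of randomised age group.
2. Report the RSV-A and RSV-B SRR differences on this set with an age-stratified Miettinen-Nurminen interval. Two strata, 50-59 and 60 or older, are enough. Show the unstratified interval alongside it for comparability with the primary analysis.
3. Label the addition post hoc if the Part A immunogenicity data are already unblinded. State that age stratification does not remove between-study differences.

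The cost is SAP wording, one derived variable, a little extra analysis, and about 0.1 to 0.2 points of power if there is no age effect. No new data are needed. The primary Group 1 versus Group 2 analysis stays as planned.

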#### 2.5.4.3. Analysis of the Key Secondary Immunogenicity Endpoints

The key secondary endpoints include the following:

- 1) GMT of serum RSV-B nAbs at Day 29
- 2) SRR in serum RSV-B nAbs at Day 29
- 3) SCR in serum influenza anti-HA Abs for each influenza strain (A/Victoria, A/Cambodia, B/Victoria, B/Phuket) at Day 29

The statistical analyses are:

- GMT of RSV-B nAbs at Day 29 will be analyzed using the same ANCOVA model as for RSV-A nAbs at Day 29. The GLSM for each vaccination group and GMR between coadministered group and mRNA-1345 plus placebo group and associated 95% CIs will be estimated from the ANCOVA model.
- SRR in RSV-B nAbs at Day 29 will be provided with 2-sided 95% CIs using the Clopper-Pearson method. The SRR difference between coadministered group and mRNA-1345 plus placebo group at Day 29 will be provided with 2-sided 95% CIs using the Miettinen-Nurminen's method.
- SCR in anti-HA Abs for each influenza strain at Days 29 will be provided with 2-sided 95% CIs using the Clopper-Pearson method. The SCR difference between coadministered

group and Afluria Quadrivalent plus placebo group at Day 29 will be provided with 2-sided 95% CIs using the Miettinen-Nurminen's method.

The key secondary endpoints of GMT and SRR, based on serum RSV-B nAbs at Day 29, will also be analyzed on the Supportive PP Set.

#### **2.5.4.4. Analysis of Other Secondary Immunogenicity Endpoints**

The secondary immunogenicity endpoints include the following:

- GMT and GMFR of post-injection/baseline titers to RSV-A nAbs up to Day 181/EoS
- GMT and GMFR of post-injection/baseline titers to RSV-B nAbs up to Day 181/EoS
- SRR and proportion of participants with  $\geq$  2-fold increases in RSV-A nAb titers up to Day 181/EoS
- SRR and proportion of participants with  $\geq$  2-fold increases in RSV-B nAb titers up to Day 181/EoS.
- SCR and proportion of participants with  $\geq$  2-fold increases in influenza anti-HA Abs for each influenza strain at Day 181/EoS
- GMT and GMFR of influenza anti-HA Abs for each influenza strain up to Day 181/EoS

The statistical analyses are:

- GMT of RSV-A nAbs, RSV-B nAbs, and influenza anti-HA Abs for each influenza strain with corresponding 95% CI will be provided at Baseline (Day 1), Day 29, and Day 181/EoS by vaccination group. The 95% CIs will be calculated based on the t-distribution of the log-transformed values and then back transformed to the original scale for presentation. The following descriptive statistics will also be provided at Baseline (Day 1), Day 29, and Day 181/EoS: the number of participants (n), median, minimum and maximum. GMT with 95% CI will be plotted at Baseline (Day 1) and Day 29 by vaccination group.
- GMFR of RSV-A nAbs, RSV-B nAbs, and influenza anti-HA Abs for each influenza strain with corresponding 95% CI will be provided at Day 29 and Day 181/EoS over pre-injection at Day 1 [baseline] by vaccination group. The 95% CIs will be calculated based on the t-distribution of the difference in the log-transformed values (post-baseline time point – Day 1) and then back transformed to the original scale for presentation. GMFR with 95% CI will be plotted at Day 29 by vaccination group.

- Proportion of participants with  $\geq$  2-fold increases from Day 1 (baseline) in RSV-A nAb titers, RSV-B nAb titers, and influenza anti-HA Abs for each influenza strain at Day 29 and Day 181/EoS will be provided with 2-sided 95% CIs using the Clopper-Pearson method by vaccination group.
- SRR in RSV-A nAb titers and RSV-B nAb titers and SCR in influenza anti-HA Abs for each influenza strain at Day 181/EoS will be provided with 2-sided 95% CIs using the Clopper-Pearson method by vaccination group.

